9.6 Reporting Procedures

9.6.1 General

Adverse events will be captured in both the source documents and on the appropriate study-specific case report forms (CRFs). Given that each of the medications being utilized in this trial has a well-established safety profile, this protocol will utilize targeted AE reporting for all non-serious adverse events, as described below.

9.6.2 AE reporting requirements

- AE of any grade that requires a modification to treatment (e.g. dose modification, dose delay, or drug discontinuation)
- All grade 3 and 4 AEs, regardless of causality
- Any clinically significant laboratory abnormality, as defined in section 8.1
- All serious adverse events (SAEs), as defined in section 8.1

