9. ADVERSE EVENTS & SAFETY MONITORING

9.1 General

Adverse event collection and reporting is a routine part of every clinical trial. This study will use the descriptions and grading scales found in the NCI Common Terminology Criteria for Adverse Events version 4.0 (CTCAE v4.0) that is available at <http://ctep.cancer.gov/reporting//ctc.html>.

Information on certain adverse events, whether reported by the participant, directly observed, or detected by physical examination, laboratory test or other means, will be collected, recorded, followed and reported as described in the following sections.

Adverse events experienced by participants will be collected and reported from initiation of study medication, throughout the study, and within 30 days of the last dose of study medication. Participants who experience an ongoing adverse event related to a study procedure and/or study medication beyond 30 days will continue to be contacted by a member of the study team until the event is resolved, stabilized, or determined to be irreversible by the participating investigator.

Participants should be instructed to report any serious post-study event(s) that might reasonably be related to participation in this study. The investigator should notify the IRB and any other applicable regulatory agency of any unanticipated death or adverse event occurring after a participant has discontinued or terminated study participation that may reasonably be related to the study.

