9.2.4 Attribution

The investigator will determine the relationship of each adverse event, if any, to investigational treatment or study procedure. Causality should be assessed using the following categories: Unrelated, Unlikely, Possible, Probable, or Definite.

The degree of certainty with which an adverse experience is attributed to drug treatment (or alternative causes, e.g. natural history of the underlying diseases, concomitant therapy, etc.) will be determined by how well the experience can be understood in terms of the following:

- Known pharmacology of the drug
- Reaction of similar nature being previously observed with this drug or class of drug
- The event having often been reported in literature for similar drugs as drug related (e.g. skin rashes, blood dyscrasias)
- The event being related by time to drug administration terminating with drug withdrawal (dechallenge) or reproduced on rechallenge.

The investigator may change his/her assessment of causality in light of follow-up information. All adverse events will be recorded, regardless of whether the event is thought to be related to investigational treatment. Attribution will be assigned as follows:

- Definite – The AE is clearly related to the study treatment.
- Probable – The AE is likely related to the study treatment.
- Possible – The AE may be related to the study treatment.
- Unlikely - The AE is doubtfully related to the study treatment.
- Unrelated - The AE is clearly NOT related to the study treatment.

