9.3 Anticipated Toxicities

If Vitamin D levels are allowed to become too high, hypercalcemia is the most common side effect. Symptoms may include anorexia, nausea, vomiting, abdominal pain, confusion, lethargy, constipation, muscle weakness, weight loss, polyuria, kidney stones, and heart arrhythmias.

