14. DATA AND SAFETY MONITORING

14.1 Data Management and Reporting

All patients who received any amount of study drug will be included in the safety analysis. Subjects will be monitored at each clinic visit and at any contact with the subject throughout the study for the occurrence of AEs and SAEs. The investigator or site staff will inquire about the occurrence of AEs/SAEs at weeks 12, 24, 36, and 52. Adverse events will be graded according to the NCI Common Terminology Criteria v. 4.0. All relevant AE's, as described in Section 9.6, that occur during active treatment will be recorded in subject source documents and on CRFs, regardless of relationship to investigational treatment. Non-serious adverse events that occur within the 30 day follow-up period will only be recorded on the CRFs if the investigator believes there to be a possible relationship to study medication. Serious adverse events should be recorded, regardless of relationship to drug.

Safety analyses will include summaries of adverse event rates (both frequency and incidence tables), baseline laboratory parameters and changes from baseline, frequency of CTC toxicity grades for both laboratory and non-laboratory data. The investigators and others responsible for patient care at individual sites should institute any supplementary investigations of major adverse events based on their clinical judgment of the likely causative factors.

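### Grade 1–2 symptoms that are not serious and do not change treatment need not be recorded, so the non-laboratory incidence and grade tables planned in section 14.1 will undercount them; section 9.2.4 says the opposite

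*Combined protocol and SAP*

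**What the plan says.** The combined protocol and SAP describes adverse event collection in several places.

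- Section 9.2.4 (Attribution): "All adverse events will be recorded, regardless of whether the event is thought to be related to investigational treatment".
- Section 9.1 is narrower and opens with "Information on certain adverse events, whether reported by the participant, directly observed, or detected by physical examination".
- Section 9.6.1 gives the well-known safety profile of the products as its reason, and states that "this protocol will utilize targeted AE reporting for all non-serious adverse events".
- Section 9.6.2 then lists four routes into the data: "AE of any grade that requires a modification to treatment"; "All grade 3 and 4 AEs, regardless of causality"; laboratory abnormalities judged significant under 8.1; and all serious events.
- Sections 6.3 to 6.5 tell sites to record and grade events by reference to 9.6.
- Section 14.1 applies the 9.6 selection to source documents as well as CRFs during active treatment. It then plans frequency and incidence tables of adverse events and "frequency of CTC toxicity grades for both laboratory and non-laboratory data".
- Section 9.3 names what is expected if vitamin D becomes too high: "Symptoms may include anorexia, nausea, vomiting, abdominal pain, confusion, lethargy, constipation, muscle weakness", among others.

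**The concern.** There are two problems. First, a site cannot follow both the unqualified rule in 9.2.4 and the selective rule in 9.6.2. With up to 5 centers, some may record everything and others only the targeted set.

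Second, if sites follow 9.6.2, as 14.1 and the visit sections direct, the planned tables have low-grade rows that the collection rule cannot fill. Nausea or constipation at grade 2 in a woman who carries on unchanged leaves no required record. Because the selection reaches back to the source documents, the event may not be recoverable later.

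What is at stake is the description of tolerability. The trial compares 50,000 IU weekly for 12 weeks with 800 IU daily, and section 14.2 asks the Data Review Committee for recommendations on safety and tolerability from cumulative toxicity data. A reader who sees a nearly empty grade 1–2 row could take it for good tolerability when it reflects the recording rule.

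**Working it through.** **Step 1: trace events through the rules.** The documents state no adverse event rate and no capture rate, so there is no planned figure to reproduce. The check is first one of text.

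| Event during treatment | Required under 9.6.2? |
|---|---|
| Any serious event, any grade | Yes |
| Grade 3–4, any cause | Yes |
| Laboratory abnormality significant under 8.1 | Yes, no grade limit |
| Non-serious grade 1–2 symptom, treatment modified | Yes |
| Non-serious grade 1–2 symptom, treatment unchanged | No |

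Only the last row is lost. Section 9.2.4 read literally would require it. Section 14.1 plans grade frequencies for non-laboratory data without saying that the low-grade rows hold only the fourth row of this table.

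The rule also changes when treatment ends. For the 30-day follow-up, sections 9.5 and 14.1 select non-serious events by possible relation to the drug and state no grade limit. Read literally, a possibly related grade 1 symptom is recorded after the last dose but not during treatment.

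**Step 2: size of the undercount (assumed inputs).** Let n be women per arm, p the true risk of a non-serious, non-laboratory grade 1–2 event (one per woman, for simplicity), and c the probability that such an event leads to a treatment change.

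- n = 93, from section 13.2.
- p = 10% to 50% and c = 5% to 20%, both assumed.
- True count = n × p: 93 × 0.10 = 9.3, up to 93 × 0.50 = 46.5 per arm.
- Recorded count = n × p × c: 93 × 0.10 × 0.05 = 0.5, up to 93 × 0.50 × 0.20 = 9.3 per arm.
- Share lost = 1 − c: 1 − 0.20 = 80%, to 1 − 0.05 = 95%.

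The share lost does not depend on p or n.

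**Step 3: effect on the comparison between arms.** Take the same true risk in both arms. The recorded risk ratio is then c(high) / c(standard).

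- Equal c: ratio 1.0. The counts are too low but the ratio is not distorted.
- c of 0.20 against 0.10: ratio 2.0 with no true difference.
- c of 0.30 against 0.10: ratio 3.0 with no true difference.
- c of 0.10 against 0.20: ratio 0.5, so the distortion can go either way.

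If the true risks differ and c is equal, the recorded risk difference is c times the true one. At c of 5–20% it shrinks to 5–20% of its true size even without any imbalance in capture.

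**Step 4: could c differ by arm?** Section 6.9.1 gives ten capsules once a week and section 6.9.3 one pill a day, with no placebo or masking described. Section 8.2 lets the physician act specifically for women on the standard dose arm, which presupposes that the arm is known. Section 6.12 leaves stopping for toxicity or for symptomatic hypercalcemia to the investigator. A difference is therefore possible, but nothing in the documents shows that it will occur.

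**The case against.** The strongest reply is that targeted collection is declared and reasoned. Section 9.1 speaks of selected events, 9.6.1 explains why, the visit sections point to 9.6, and 14.1 invokes 9.6 before it describes its tables. Read in that order, 14.1 tabulates the targeted set, and the sentence in 9.2.4 concerns relatedness rather than grade. The main expected toxicity is also measured independently of discretion: calcium, albumin and 25(OH)D are drawn at baseline and weeks 4, 12, 24, 36 and 52 in both arms. Calcium kidney stones lead to removal from the study under 9.4, so they are captured at any grade. No listed objective is a safety comparison, and the monthly safety meeting sees clinical data on all participants.

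Much of this stands. Targeted reporting is a legitimate choice, the gap is confined to one class of event, and the 9.2.4 conflict alone would need only an edit. The reply does not remove the problem that 14.1 plans unlabelled low-grade rows made up of events selected by what was done about them.

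Some stronger readings are tempting but not supported:

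- A reader might infer that the arms will not be comparable. The same recording rule applies to both, so this holds only if the probability of a treatment change differs.
- A reader might cite 8.1 as giving the high-dose arm more holds and reductions. Its triggers are laboratory values only, with the same thresholds for every patient. The high-dose arm has two versions of the reduced dose because it has two phases.
- A reader might call the trial open label. The documents do not say so; it is an inference from the regimens.
- A reader might say that low-grade events enter only through a treatment change. Serious events and 8.1 laboratory abnormalities enter as well.

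**Conclusion.** The point holds, within limits. Sections 9.2.4 and 9.6.2 conflict as worded. Under the rule that 14.1 adopts, non-serious, non-laboratory grade 1–2 events without a treatment change are not required to be recorded. The corresponding rows and the overall incidence figures will understate the truth wherever such events occur. The size cannot be read from the documents; the 80–95% loss rests entirely on the assumed 5–20% probability of a treatment change. Different capture by arm is a credible risk whose direction and size are unknown. Grade 3–4 and serious events are unaffected, laboratory grades can be derived from the scheduled values, and the primary endpoint is measured separately. The point is worth correcting because it decides what the safety tables can validly show.

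**What to change.** 1. Reconcile 9.2.4, 9.6.2 and 14.1 so that one recording rule applies during treatment, and state how it relates to the 30-day rule in 9.5. In the same edit, correct the reference in 9.6.2 that sends the reader to 8.1 for the definition of a serious event; the definition is in 9.2.2.
2. In 14.1, restrict between-arm non-laboratory tables to grade 3 or higher and serious events. Show lower-grade events that modified treatment in a separate table, labelled as a selected subset.
3. Preferably, add to 9.6.2 the recording of the 9.3 symptoms at any grade, whether or not treatment changes. Use a fixed checklist asked in identical words in both arms at the adverse event visits already planned for weeks 12, 24, 36 and 52. Those symptoms can then enter the all-grade tables, and targeted reporting stays for everything else.

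Arthralgia does not need to be on the checklist, since the HAQ-II and its pain scale already measure it.

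Items 1 and 2 cost only wording. Item 3 costs a short CRF page, a few minutes per visit and some extra low-grade data entry. None of the three alters a dose, a hold or a stopping rule.

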9.6.3 Serious Adverse Events

Any serious adverse events that occur during the clinical study or within 30 days of receiving the last dose of study medication, whether or not related to the study drug, must be reported by the

investigator. In addition, any SAEs which occur as a result of protocol specific diagnostic procedures or interventions must also be reported.

All serious adverse events must be reported to the PI within 1 business day of becoming aware of the event. The protocol chair will then report SAEs to the Baylor College of Medicine IRB, in accordance with standard operating procedures. Events should be reported using a MedWatch form (FDA Form 3500), which is available for download on the FDA website.

The SAE report should comprise a full, written summary detailing relevant aspects of the adverse events in question. Where applicable, information from relevant hospital case records and autopsy reports should be included. Follow-up information and follow-up reports should be forwarded to all appropriate entities within 24 hours.

Instances of death, if brought to the attention of the investigator AT ANY TIME after cessation of study medication, and linked by the investigator to a previous clinical trial, should be reported to the FDA.

The PI will disseminate information regarding serious adverse events to the participating investigators within 5 days of review of the information by the Protocol Chair (or designee in the event of extended absence) only in the case that the event(s) is believed to be related (i.e., possibly, probably, or definitely) to the study medication.

9.6.4 Institutional Review Board

All adverse events and serious adverse events will be reported to the IRB per current institutional standards. If an adverse event requires modification of the informed consent, these modifications will be provided to the IRB with the report of the adverse event. If an adverse event requires modification to the study protocol, these modifications will be provided to the IRB as soon as possible.

9.6.5 Food and Drug Administration (FDA)

In this trial, unexpected adverse events believed to be definitely, probably, or possibly related to the medications will be reported to the Food and Drug Administration via MedWatch (using the online

form available at <https://www.accessdata.fda.gov/scripts/medwatch/>; by telephone [name]; or by fax [name]. FDA Form 3500A — Mandatory Reporting, available at: <http://www.fda.gov/medwatch/report/hcp.htm>.

10. CORRELATIVE/SPECIAL STUDIES

10.1 Grip Strength

To further investigate whether grip strength may serve as a simple, objective measure of AIA, we will measure grip strength at baseline, week 12 and week 52 visits (see study Calendar in Appendix B), and see whether changes in grip strength do correlate with changes in joint pain, as represented in the HAQ score. Research coordinators will measure grip strength as outlined in [Section 6.8.2](#).

11. SPECIMEN BANKING

Any leftover study blood samples may be stored for future research studies. The subjects will consent to the future use of samples in the consent form for the study. All samples will be stored indefinitely in the Lester & Sue Smith Breast Center Tumor Bank, located at [name]. Samples will not contain any traditional patient identifiers; however, samples will be coded such that specimens are traceable back to the patient. The link between the specimen code and the patient will be maintained in a secure area, accessible only to the Tissue Bank Coordinator. Samples will only be released for use in future studies after approval by the protocol chair and other regulatory bodies, as appropriate. The samples will not be sold to third parties.

12. MEASUREMENT OF EFFECT

The primary assessments for this study will be the average score on the Health Assessment Questionnaire (HAQ-II), as well as the score from the visual analog scale.

12.1 Definitions

12.1.1 **Evaluable for toxicity:** All patients will be evaluable for toxicity from the time of their first treatment with Vitamin D.

12.1.2 **Evaluable for response:** All the patients who have been randomized will be considered evaluable for response, regardless of how much treatment they have received,

consistent with an intention to treat analysis. These patients will have their response classified according to the definitions stated below. Any patient who began the study medication, but does not complete the HAQ at 12 weeks, will be deemed to be a study failure (i.e. the development of AIA will be assumed), consistent with an intention to treat analysis.

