6.8 On Study Assessments and Procedures

6.8.1 Health Assessment Questionnaire

Each subject will be asked to complete the Health Assessment Questionnaire (HAQ-II) at baseline, 12 weeks, and 52 weeks. The questionnaire will be completed in the office, during the clinic visit, and it will be administered by the study coordinator. Generally, the questionnaire can be completed in less than 5 minutes by most patients. The questionnaire will be available in English, Spanish, and Vietnamese.

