6.12 Discontinuation of Treatment

In the event that study treatment is discontinued prematurely, subjects should undergo the study procedures as described in Section 6.5. NOTE: Subjects who discontinue study therapy will still be included in the overall evaluation of response (intent-to-treat analysis), regardless of the reason for therapy discontinuation. Study treatment may be discontinued for any of the following reasons.

- Breast cancer recurrence or new breast cancer
- Failure of the subject to attend the majority of scheduled visits. The protocol chair or her designee will determine when non-compliance with clinic visits should lead to removal from study.
- Lost to follow-up
- Withdrawal of consent.
- Unacceptable major toxicity, as determined by the treating investigator.
- Intercurrent illness or condition that would, in the judgment of the treating investigator, affect assessment of clinical status to a significant degree or require discontinuation of study treatment.
- At subject's own request. Note: The reason for discontinuation from the study must be documented.

- Study is closed for any reason (e.g. new information shows that the patient's welfare would be at risk if she continued study treatment).
- General or specific changes in the participant's condition which render the participant unacceptable for further treatment in the opinion of the treating investigator physician.
- 25-hydroxyvitamin D level exceeds 120 ng/mL at any point during the study
- 25-hydroxyvitamin D level is persistently >70 ng/mL, as outlined in [Section 8.1](#).
- Corrected calcium level >11.0 mg/dL on any measurement during the study, or corrected calcium level >10.5 mg/dL on three consecutive measures, as outlined in [Section 8.1](#).
- Symptomatic hypercalcemia which warrants discontinuation, at the discretion of the treating investigator physician, with symptoms including but not limited to confusion, lethargy, constipation, nausea/vomiting, abdominal pain, or muscle weakness.
- Development of symptomatic calcium-based renal stones

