6.13 Withdrawal from Study

Subjects may be withdrawn from follow-up for the following reasons:

- Subject withdraws consent for follow-up.
- Subject is lost to follow-up (after at least three documented attempts to contact her).
- Study is terminated for any reason.
- Subject death

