6.14 Criteria for Removal from the Study

Participants will be removed from study when any of the criteria listed in Section 6.12 applies. All patients who are randomized in the study will be included in the overall evaluation of response (intent-to-treat analysis). All reasons for discontinuation of therapy should be documented clearly in the medical record.

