8. DOSING DELAYS/DOSE MODIFICATIONS

8.1 Dose Modifications/Delays

For any patient in the study, if 25-hydroxyvitamin D level exceeds 120 ng/mL at any point, the patient will be taken off the study medication. If the 25 (OH)D level is >90 ng/mL, we will hold the vitamin D supplementation for 4 weeks, and then recheck vitamin D level. If it is <70 ng/mL after 4 weeks, the patient may resume vitamin D at 50,000 IU every other week if the patient was on the lead-in phase of the high dose arm. If the patient was on the continuation phase of the high dose arm, she would instead take 1000 IU/day. If the patient was on the standard dose arm, she would take Caltrate-D once every other day. If the 25-hydroxyvitamin D level did not fall to <70 ng/mL after 4 weeks of a drug holiday, then the vitamin D will be held for an additional 4 weeks. At the end of this 8 week period, patients will resume reduced vitamin D dosing as described above if the level has fallen to <70 ng/mL. However, if the level is still ≥70 ng/mL, then the patient will be taken off the study medication.

Similarly, if the calcium level is >11.0 mg/dL at any time during the study, the patient will be taken off the study. If the calcium level is between 10.5 and 11.0 mg/dL, the patient may follow the same vitamin D reduction schedule outlined above in which the vitamin D supplementation is held for 4 weeks, and may only be resumed at half dose if the calcium level is within normal limits, according to reference lab values. If the calcium level has not normalized after 8 weeks of drug holiday, then the patient will be taken off the study medication.

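### The plan conflicts on whether stopping study vitamin D ends participation; read literally, it would score an early stopper as AIA although her week-12 outcome could have been measured

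*Combined protocol and SAP*

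**What the plan says.** **Passages that tie a stop to leaving the study.** Section 6.14: "Participants will be removed from study when any of the criteria listed in Section 6.12 applies". Section 6.12 is the list of reasons for discontinuing treatment, yet its own-request item adds: "The reason for discontinuation from the study must be documented". Section 8.1 takes a woman with calcium above 11.0 mg/dL off the study, and 9.4 does the same for calcium kidney stones. Section 6.12 lists those events (corrected calcium above 11.0; symptomatic calcium-based stones) as reasons to stop treatment. Appendix B, footnote 4, takes a woman off trial if the bone density test is late.

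**Passages that keep the two apart.** Section 6.13 opens its own, shorter list with "Subjects may be withdrawn from follow-up for the following reasons": consent withdrawn, lost to follow-up, study terminated, death. For 25(OH)D, 8.1 says "if 25-hydroxyvitamin D level exceeds 120 ng/mL at any point, the patient will be taken off the study medication". Section 6.7 follows all subjects for recurrence, and Appendix B, footnote 2, requires safety follow-up after early discontinuation.

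**Outcome collection and scoring.** Section 6.8.1: "Each subject will be asked to complete the Health Assessment Questionnaire (HAQ-II) at baseline, 12 weeks, and 52 weeks". Section 6.12: "In the event that study treatment is discontinued prematurely, subjects should undergo the study procedures as described in Section 6.5". The 6.5 visit includes an HAQ-II, but it is timed five to ten business days after therapy ends. Section 6.14 also says "All patients who are randomized in the study will be included in the overall evaluation of response (intent-to-treat analysis"). Section 12.1.2 calls every randomised woman evaluable, then adds: "Any patient who began the study medication, but does not complete the HAQ at 12 weeks, will be deemed to be a study failure".

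**The concern.** Keeping a woman in the intent-to-treat evaluation does not ensure that her outcome is measured, because 12.1.2 can keep her there by assumption. No passage says that the week-12 HAQ-II is still collected after a stop, or how the HAQ-II from the 6.5 visit is used. A site that follows 6.14 to the letter would have no week-12 questionnaire for a woman who stopped, say, at week 6, and she would become an AIA case. A site that follows 6.8.1 would measure her. The study may run at up to five centers, so the same event could be scored in two ways. For these women the primary endpoint would record the stop and not joint pain.

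There is a smaller gap beside it. The missing-questionnaire rule covers only women who began study medication. A randomised woman who never starts and has no week-12 HAQ is called evaluable but has no stated outcome.

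**Working it through.** **1. Which women are exposed.** Only stops before week 12, in women who began vitamin D, can alter the primary endpoint.

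- Laboratory routes: week 4 is the only scheduled on-treatment laboratory visit before week 12. A single 25(OH)D above 120 ng/mL or calcium above 11.0 mg/dL found there counts.
- Hold routes in 8.1: a week-4 sample plus two 4-week holds ends at 4 + 4 + 4 = week 12. The week-4 window is ±5 business days, so a sample drawn a week early brings this to about week 11. With the 8.1 rechecks, a third consecutive calcium above 10.5 mg/dL has the same timing.
- Other routes: own request, toxicity, intercurrent illness, symptomatic events and the late bone scan.
- Consent withdrawal and loss to follow-up also fall before week 12, but no rewording would recover those questionnaires.

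**2. Reproduce the plan's sample size.** Inputs from 13.2: 33% vs 19%, one-sided α = 0.10, 80% power, chi-square test. With pooled variance and no continuity correction,

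n = [z₀.₉₀·√(2p̄(1−p̄)) + z₀.₈₀·√(p₁(1−p₁)+p₂(1−p₂))]² / (p₁−p₂)², p̄ = 0.26

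= [1.2816 × 0.6203 + 0.8416 × 0.6124]² / 0.14² = 1.717 / 0.0196 = 87.6, so 88 per arm. This matches the 88 in 13.7.

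**3. Power with default scoring.** Method: exact binomial enumeration at 93 per arm, rejecting when the pooled Z is at least 1.2816, single look, ignoring the futility analysis. With none missing, power is 82.3% (80.4% at 88 per arm). If missingness is unrelated to AIA and a share m of an arm is scored as AIA by default, the scored rate is p(1−m) + m. One woman is m = 1/93 = 0.0108. For example, one high-dose woman gives 0.19 × 0.9892 + 0.0108 = 19.9%.

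| Avoidable stops scored as AIA (hypothetical) | Scored rates, standard vs high | Power | Power on top of 5% dropout in each arm |
|---|---|---|---|
| None | 33.0% vs 19.0% | 82.3% | 76.2% |
| One, high-dose arm only | 33.0% vs 19.9% | 78.1% | 71.6% |
| One in each arm | 33.7% vs 19.9% | 81.1% | 74.8% |
| One, standard arm only | 33.7% vs 19.0% | 84.9% | 79.2% |

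The last column scores the plan's own 5% dropout (13.2; 0.05 × 93 = 4.65 women per arm) as AIA as well, so its base rates are 36.35% vs 23.05%.

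**4. If women with missing questionnaires are more likely to have AIA.** Hold the overall rates at 33% and 19%, and let q be the share of missing women who truly have AIA. The scored rate is then p + m(1−q). At q = 0.5, one high-dose stop moves power from 82.3% to 79.8% (80.4% to 77.8% on top of 5%). At q = 1 nothing changes.

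Only the 5% and the 88 are the plan's figures. The single extra stops and q are assumptions.

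**The case against.** The best defence is that 6.14 uses removal as shorthand for stopping therapy. Its second sentence keeps all randomised women in the evaluation, and its third asks for the reasons for discontinuing therapy. Section 6.13 does not list a treatment stop as a reason to leave follow-up. Section 9.4 continues to follow a woman with high calcium until the level normalises. Section 6.8.1 says each subject. The default in 12.1.2 is triggered by an absent questionnaire and not by a stop, so a woman who stops and still completes the week-12 HAQ-II is already scored on what was observed. Section 13.4 fixes week 12 as primary, so nothing suggests that the 6.5 questionnaire replaces it.

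Most of this stands, and it shows the probable intent. A reader might therefore infer too much from 6.14 alone, namely that the plan means to abandon outcome collection after a stop. The documents do not support that. What the defence does not remove is the literal instruction in 6.14, repeated in 8.1, 9.4 and the calendar footnote, with no sentence telling a site which reading governs the week-12 questionnaire.

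A reader might also infer that default scoring works against the high-dose arm, since the laboratory stopping criteria could plausibly be met more often there. The documents give no stop rates by arm, several routes are unrelated to dose, and a stop in the standard arm alone moves power the other way.

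**Conclusion.** The conflict is real and reaches the primary endpoint, but its likely effect is small. At the plan's design rates, each single-arm avoidable stop shifts power by between a gain of about 3 points and a loss of about 5. The shift is smaller if women with missing questionnaires are more likely to have AIA, and nil if all of them do. A gain is no reassurance: in either direction a woman whose joint pain could have been measured is misclassified. The number of such women is unknown and probably very few.

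Two stronger readings should be set aside. The fall from 82.3% to 76.2% under the plan's 5% dropout is not a cost of this conflict: it comes mainly from the scoring rule applied to dropout that clearer wording may not recover. Nor does the point show that scoring a missing questionnaire as AIA is wrong. That rule is prespecified and can stay; the issue is avoidable missingness feeding it.

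These figures assume true rates of 33% and 19%, a single look, and the hypothetical stops in the table. Label: cheap improvement, low to moderate priority.

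**What to change.** - Reconcile 6.12, 6.13, 6.14, 8.1, 9.4 and Appendix B footnote 4, so that stopping study vitamin D is distinguished from withdrawing from follow-up. No threshold or clinical rule needs to change.
- State in 6.8.1 and 6.12 that the week-12 and week-52 HAQ-II are collected from every randomised woman regardless of treatment status, unless she withdraws consent. State that the observed week-12 HAQ-II is used for the primary endpoint, and that the early-stop HAQ-II of 6.5 does not replace it.
- Secondary: in 12.1.2, define the outcome for a randomised woman who never starts and has no week-12 HAQ. Report missing week-12 HAQs by arm and reason.

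The cost is amendment wording, plus one questionnaire of about five minutes, at an already scheduled time, for the few women who stop before week 12. No sample-size figure changes.
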